10.9. Pharmacokinetic Analysis

The pharmacokinetic data will not be evaluated within the outputs outlined within this SAP. Instead the summary and analysis of these outputs will be outlined within a separate analysis plan.

10.10. Immunogenicity Analysis

The anti-drug antibodies data will not be evaluated within the outputs outlined within this SAP. Instead the summary and analysis of these outputs will be outlined within a separate analysis plan.

10.11. Safety Analysis

All analyses of safety endpoints will be descriptive and will use the Safety Analysis Set. No formal statistical analysis of safety data will be performed.

10.11.1. *Adverse Events*

Adverse event (AE) data presentations will be produced for adverse events that occur during the study.

All adverse events will be coded using MedDRA, Version 26.0.

An adverse event is defined as treatment emergent if the onset date is on or after the date of first dose of study drug up to 100 days after the last dose of study drug and before starting any subsequent cancer treatment. Should any onset date for an adverse event be missing or only a partial date recorded (such that it cannot be determined if the event onset was prior to the date of first dose) then it will be assumed that the event is treatment emergent, unless the adverse event stop date indicates otherwise. Any adverse event with an onset date earlier than the date of first dose of study drug will be classified as a pre-treatment adverse event and will be identified in subject listings only.

A summary of treatment-emergent AEs will be presented by cohort showing the number of subjects with events (also split by severity; mild, moderate, severe), number of subjects with SAEs, number of subjects with related events and number of subjects with events leading to early withdrawal from the study.

Additionally, each of the summaries below will be presented for treatment emergent AEs:

- Adverse Events by cohort, System Organ Class (SOC) and Preferred Term (PT).
- Adverse Events by cohort, SOC, PT and severity.
- Adverse Events related to study drug by cohort, SOC and PT:
 - etigilimab
 - nivolumab
 - etigilimab and nivolumab
 - etigilimab or nivolumab
- Serious Adverse Events by cohort, SOC and PT.
- Serious Adverse Events related to study drug by cohort, SOC and PT:
 - etigilimab
 - nivolumab
 - etigilimab and nivolumab
 - etigilimab or nivolumab
- Adverse Events that led to death by cohort, SOC and PT.
- Adverse Events that led to treatment discontinuation by cohort, SOC and PT.
- Adverse Events that led to withdrawal from the study by cohort, SOC and PT.
- Adverse Events of Grade 3 or Higher by cohort, SOC and PT.
- Adverse Events of Special Interest by cohort, SOC and PT:

- Infusion Related Adverse Events
- Immune Related Adverse Events
- Infusion or Immune Related Adverse Events

Additionally an overall summary of treatment emergent adverse events that occur within 100 days of last dose of study drug regardless of whether they receive any subsequent cancer treatment between last dose of study drug and the adverse event will be presented, along with a summary of these by SOC and PT.

Listings will be provided for AEs, serious adverse events (SAEs), adverse events directly resulting in discontinuation of study drug or withdrawal from study.

Tables presented by relationship will only include the subset of adverse events that are judged as being 'Related' to study drug (etigilimab, nivolumab, either or both).

If a subject experiences more than one AE with the same preferred term, that preferred term will be counted only once. It will be assigned the greatest observed severity and the strongest relationship to viral challenge among those events for the tables in which those characteristics are summarised.

In all AE summary tables results will be displayed ordered in terms of decreasing frequency of SOC occurrence (based on total across all subjects), and within each SOC also ordered in terms of decreasing frequency of preferred term occurrence (also based on total across all subjects). In all AE summary tables a total column including data across all subjects will also be presented.

10.11.2. *Laboratory Variables*

The following haematology, biochemistry, coagulation, viral serology and urinalysis parameters (as shown within the protocol) will be included within subject listings (and presented in the units as shown) and summary tables where relevant:

- Haematology: Red blood cell (RBC) count ($10^{12}/L$), mean cell haemoglobin (MCH) (pg), mean cell volume (MCV) (fL), hematocrit, haemoglobin (g/L), platelet count ($10^9/L$), white blood cell (WBC) count (absolute) ($10^9/L$), neutrophils (% and absolute ($10^9/L$)), lymphocytes (% and absolute ($10^9/L$)), monocytes (% and absolute ($10^9/L$)), eosinophils (% and absolute ($10^9/L$)), basophils (% and absolute ($10^9/L$)).
- Biochemistry: Alanine transaminase (ALT) (IU/L), albumin (g/L), alkaline phosphatase (ALP) (IU/L), aspartate transaminase (AST) (IU/L), bicarbonate (mmol/L), total bilirubin (umol/L), blood urea nitrogen (BUN) (mmol/L), calcium (mmol/L), chloride (mmol/L), creatinine (umol/L), glucose (mmol/L), lactate dehydrogenase (LDH) (IU/L), magnesium (mmol/L), potassium (mmol/L), phosphate (mmol/L), total protein (g/L), sodium (mmol/L), carbon dioxide (mmol/L).
- Coagulation: prothrombin time (PT) (secs), activated partial thromboplastin time (APTT) (secs), International normalised ratio (INR).
- Thyroid Function Tests: Thyroid Stimulating Hormone (TSH), Free Triiodothyronine (T3), Free Thyroxine (T4).
- Other: β -HCG.
- Urinalysis: Specific gravity, pH, blood, glucose, protein, ketones.
- Urinalysis (microscopy): Urine RBC (/HPF), Urine WBC (/HPF), bacteria, casts and epithelial cells.

Laboratory data collected in different units to that shown will be converted to the above specified units (if possible) for presentation in subject Listings.

Summary statistics for absolute and changes from baseline by scheduled timepoint will be tabulated, by cohort, for haematology, biochemistry, thyroid function tests and coagulation. Baseline here will be the last non-missing measurements taken prior to the first infusion of etigilimab.

Laboratory parameters (Haematology, Biochemistry, Thyroid function tests, Coagulation, Urinalysis and Urinalysis (microscopy), where done) will be included in subject listings. Laboratory values outside the normal range will be identified in subject listings as above or below the normal range, and, where available, the CTCAE Toxicity Grade will be listed.

Unscheduled visit assessments will be included within subject listings.

10.11.3. *Vital Signs*

Vital signs will be measured at every visit throughout the trial. Specifically vital signs being measured prior to infusion of etigilimab, every 15 mins during the infusion and 30 and 60 mins after infusion for the first infusion with etigilimab. For subsequent infusions with etigilimab vital signs will be measured prior to infusion and 30 mins post-infusion.

Summary statistics for absolute and changes from baseline will be tabulated, by scheduled timepoint and by cohort, for vital signs parameters (systolic blood pressure (SBP) (mmHg), diastolic blood pressure (DBP) (mmHg), pulse rate (beats/min), respiratory rate (breaths/min), and temperature) and will be included within subject listings. Baseline vital signs are the last non-missing values taken prior to the first infusion with etigilimab.

10.11.4. *Physical Examination*

Any physical examination findings are reported as Adverse Events and will be listed there.

10.11.5. *ECOG Performance Status*

Eastern Cooperative Oncology Group (ECOG) Performance is rated from Grade 0 to Grade 5, as per the table below. ECOG performance status will be summarised as a shift from the status at baseline and will also be listed.

10.11.6. *12-Lead ECG*

ECGs will be carried out at screening, 30 mins post-infusion on Cycle 1 Day 1, 30 mins post-infusion on Cycle 4 Day 1 and at treatment termination. Baseline will be the last non-missing results observed prior to infusion on Cycle 1 Day 1.

Summary statistics for absolute values and change from baseline by scheduled time point will be tabulated, by cohort and for all subjects, for ECG parameters (PR interval, QRS duration, QTc interval (sec) and QTcF interval (sec)).

10.11.7. *Contrast Enhanced Head CT or MRI Scan*

Any data collected for this test will be listed.

11.CHANGES TO THE PROTOCOL SPECIFIED ANALYSIS DETAILED IN THE STATISTICAL ANALYSIS PLAN

An additional definition of Treatment Emergent Adverse Event was added to the SAP:

Any adverse event that occurs after first dose of study treatment and within 100 days of last dose of study treatment regardless of whether they receive any subsequent cancer treatment between last dose of study drug and the adverse event.

Toxicity grades of laboratory parameters are not summarised.

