8.3.1.1 Time Period and Frequency for Collecting AE and SAE Information

All AEs will be collected from the start of treatment with etigilimab until 90 days after the treatment termination visit and at the timepoints specified in the SoA. SAEs will be collected starting after signature of the informed consent until 90 days after the treatment termination visit.

Medical occurrences that begin before the start of study treatment but after obtaining informed consent will be recorded on the Medical History/Current Medical Conditions section of the case report form (CRF).

All SAEs will be recorded and reported to the sponsor or designee within 24 hours, as indicated in [Appendix 4](#). The investigator will submit any updated SAE data to the sponsor within 24 hours of it being available.

Investigators are not obligated to actively seek AE or SAE information in former study subjects. However, if the investigator learns of any SAE, including a death, at any time after a subject has been discharged from the study, and he/she considers the event to be reasonably related to the study treatment or study participation, the investigator must promptly notify the sponsor.

The method of recording, evaluating, and assessing causality of AE and SAE and the procedures for completing and transmitting SAE reports are provided in [Appendix 4](#).

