9.3.2. Safety Analyses

Adverse events will be coded using the Medical Dictionary for Regulatory Activities (MedDRA) version 18.0 or higher and will be graded according to the NCI-CTCAE, v 4.03 or higher.

Summaries of AEs will be based on TEAEs. A TEAE is an AE that emerges or worsens in the period from the first dose of study treatment etigilimab or nivolumab, whichever is earlier, to 100 days after the last dose of etigilimab or nivolumab (whichever is dosed last) or until starting another treatment.

TEAEs will be summarized by treatment group and by the frequency of subjects experiencing TEAEs corresponding to MedDRA system organ classes and preferred terms.

Separate tabulations will also be produced for TEAEs assessed as related to study drug(s), TEAEs that led to treatment discontinuation, TEAEs that led to death, and TEAEs \geq Grade 3 in severity. Treatment-emergent serious AEs and SAEs related to study drug(s) will also be tabulated.

Laboratory results (hematology, serum or plasma chemistry, and coagulation) and the corresponding change from baseline values will be summarized by group and scheduled timepoint. A shift table, tabulation for baseline to each scheduled assessment and the worst post treatment value according to the CTCAE grade, will be provided for selected clinical laboratory tests. Laboratory results together with the normal ranges and CTCAE grade will be listed. Laboratory values that are below or above the normal ranges will be flagged.

Vital signs and ECGs and the corresponding changes from baseline will be summarized by group and scheduled timepoint.

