
Etigilimab and Nivolumab	X (XX.X)							
Etigilimab or Nivolumab	X (XX.X)							
Subjects with any SAEs leading to Death	X (XX.X)							
Subjects with any AESIS	X (XX.X)							
Subjects with any AESI Immune Related Adverse Event	X (XX.X)							
Subjects with any AESI Infusion Reaction	X (XX.X)							

TEAE = Treatment Emergent Adverse Event; SAE = Serious Adverse Event; AESI = Adverse Events of Special Interest;

NCI CTCAE = National Cancer Institute Common Terminology Criteria for Adverse Events (version 5.0)

Note: A TEAE is an AE that emerges or worsens in the period from the first dose of study drug to 100 days after the last dose of study drug.

Note: A TEAE is considered related to study drug if relationship is missing.

Note: No subjects were recruited into Cohort D and so this cohort is not displayed.

Note: Percentages are based on the safety analysis set.

Source: Listing 16.2.7

The Table shell will be used for

Table 14.3.1.9 Overall Summary of Treatment Emergent Event Regardless of Subsequent Cancer Treatment by System Organ Class and Preferred Term.

Table 14.3.1.2
Treatment Emergent Adverse Events by System Organ Class and Preferred Term
Safety Analysis Set

System Organ Class Preferred Term [1]	Cohort A EC CPI-Naive (N = XX) n (%)	Cohort B		Cohort C Cervical (N = XX) n (%)	Cohort E TMB-H/MSS (N = XX) n (%)	Cohort F Rare Tumors (N = XX) n (%)	Cohort G Post-CPI (N = XX) n (%)	Cohort H Ovarian (N = XX) n (%)	Total (N = XX) n (%)
		Head and Neck (N = XX) n (%)	Cohort B Cervical (N = XX) n (%)						
Number of TEAE	XX	XX	XX	XX	XX	XX	XX	XX	XX
Number of Subjects with any TEAE	XX (XX.X)	XX (XX.X)	XX (XX.X)	XX (XX.X)	XX (XX.X)	XX (XX.X)	XX (XX.X)	XX (XX.X)	XX (XX.X)
System Organ Class 1	X (XX.X)	X (XX.X)	X (XX.X)	X (XX.X)	X (XX.X)	X (XX.X)	X (XX.X)	X (XX.X)	X (XX.X)
Preferred Term 1	X (XX.X)	X (XX.X)	X (XX.X)	X (XX.X)	X (XX.X)	X (XX.X)	X (XX.X)	X (XX.X)	X (XX.X)
Preferred Term 2	X (XX.X)	X (XX.X)	X (XX.X)	X (XX.X)	X (XX.X)	X (XX.X)	X (XX.X)	X (XX.X)	X (XX.X)
System Organ Class 2	X (XX.X)	X (XX.X)	X (XX.X)	X (XX.X)	X (XX.X)	X (XX.X)	X (XX.X)	X (XX.X)	X (XX.X)
Preferred Term 1	X (XX.X)	X (XX.X)	X (XX.X)	X (XX.X)	X (XX.X)	X (XX.X)	X (XX.X)	X (XX.X)	X (XX.X)
Preferred Term 2	X (XX.X)	X (XX.X)	X (XX.X)	X (XX.X)	X (XX.X)	X (XX.X)	X (XX.X)	X (XX.X)	X (XX.X)

[1] MedDRA Version 26.0.

TEAE = Treatment Emergent Adverse Event.

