Cohort/ Subject Number	MedDRA SOC / Preferred Term [1] / Adverse event (verbatim)	Start Date (Study Day) / Stop Date (Study Day)	TE [2] / TE_S [3] / NCI CTCAE Grade [4]	SAE / Serious Criteria [5]	Infusion Reaction? / Infection or Infestation?	AESI Infusion Immune	Related to: Etig/ Nivo/ Both	Outcome [6] / Action Taken Etig [7] / Nivo [7] / Other Action [8] /	Comments
XXX / XXXXX	XXXXXXXXX/ XXXXXX/ XXXXXX	DDMMYYYY (XX) / DDMMYYYY (XX)	Yes or No / Yes or No / X	Yes or No / XX	Yes or No / Yes, Yes COVID or No	Yes or No/ Yes or No	Related or Not Related/ Related or Not Related/ Related or Not Related	X / X / X / X	XXXXXXXXX XXXXXXXXX

NA = Not applicable, TE = Treatment Emergent, SAE = Serious Adverse Event, AESI = Adverse Event of Special Interest, NCI CTCAE = National Cancer Institute Common Terminology Criteria for Adverse Events (version 5.0).

[1] MedDRA Version 26.0.

[2] An AE occurring on or after the first dose of study drug and within 100 days of last dose of study drug.

[3] An AE occurring on or after the first dose of study drug, within 100 days of last dose of study drug and regardless of any other subsequent cancer treatment.

[4] Grade 1 = Mild, Grade 2 = Moderate, Grade 3 = Severe, Grade 4 = Life threatening, Grade 5 = Fatal.

[5] 1 = Death; 2 = Life-threatening; 3 = Hospitalization; 4 = Persistent or significant disability/incapacity; 5 = Congenital anomaly/birth defect; 6 = Other.

[6] Outcome: 1 = Resolved; 2 = Resolved with Minor Sequelae; 3 = Resolved with Major Sequelae; 4 = Ongoing; 5 = Fatal; 6 = Unknown.

[7] Action Taken: 1 = None; 2 = Dose held; 3 = Infusion interrupted; 4 = Drug permanently discontinued, 5 = Not applicable

[8] Other Action: 1 = None; 2 = Non-drug therapy given; 3 = Concomitant medication taken; 4 = Diagnostic procedure performed; 5 = Subject withdrawn; 6 = Subject hospitalized; 7 = Other.

Listing 16.2.8.1
Haematology

Cohort/ Subject Number	Visit	Collection Date (Study Day)	Parameter	Result	Change from Baseline	Units	Lower Limit	Upper Limit	Flag	Comments
XXXXX / XXXXX	XXX	DDMMYYYY (xx)	Basophils (abs)	X.XX	X.XX	X10 ⁹ /L	X.XX	X.XX	L / H	XXXXXXXXXXXX

Flag: L = below lower limit, H = above upper limit. # = Baseline.

Note: Values prefixed with < are treated as 0 when calculating the change from baseline.

Programming Note: The parameters should be listed in the order that they appear in the protocol.

Programming Note: # should be placed against the baseline measurement for each parameter.

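### SAP 10.11.1 drops worsening from the protocol's definition of a treatment-emergent adverse event without declaring it, while the SAP's own table footnotes still count worsening

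*SAP*

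**What the plan says.** Protocol 9.3.2 (Safety Analyses) says: "A TEAE is an AE that emerges or worsens in the period from the first dose of study treatment". The period ends 100 days after the last dose or when another treatment starts. The synopsis in Appendix 9 repeats this.

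SAP 10.11.1 gives a different rule: "An adverse event is defined as treatment emergent if the onset date is on or after the date of first dose of study drug". The upper limits are 100 days after the last dose and the start of subsequent cancer treatment. Of an event with onset before first dose, it says that it "will be classified as a pre-treatment adverse event and will be identified in subject listings only". No exception is made for an event that later gets worse.

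The SAP shells for Tables 14.3.1.1, 14.3.1.2 and 14.3.1.3 carry the footnote "A TEAE is an AE that emerges or worsens in the period from the first dose of study drug", which keeps the protocol's wording. Listing 16.2.7 note [2] defines the treatment-emergent flag as "An AE occurring on or after the first dose of study drug and within 100 days of last dose of study drug", with no mention of worsening.

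SAP Section 4 commits to listing departures from the protocol's analyses in Section 11. Section 11 has two entries. One says that laboratory toxicity grades are not summarised. The other adds a second TEAE definition that ignores subsequent cancer treatment: "Any adverse event that occurs after first dose of study treatment and within 100 days of last dose of study treatment". Neither mentions the loss of worsening.

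**The concern.** The programmer is given two rules. The body text and the listing note say onset or occurrence after first dose; the table footnotes say onset or worsening. If the body text is followed, each AE table prints a definition that its program does not apply, and a reader of the study report has no way to see this.

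At stake is the completeness of a secondary safety endpoint. A serious event that begins during screening, for example a complication of a screening biopsy, and becomes more severe or fatal after dosing is a TEAE under the protocol. Under SAP 10.11.1 it would be missing from the overall, serious and fatal TEAE tables and from the Grade 3 or higher counts.

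**Working it through.** No figure in the plan is in dispute, so the check compares the texts and then traces which records each rule keeps.

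**Step 1. The definitions side by side.**

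| Place | Counts worsening? | End of window |
|---|---|---|
| Protocol 9.3.2 and synopsis | Yes | 100 days after last dose, or start of another treatment |
| SAP 10.11.1, main definition | No | 100 days after last dose, and before subsequent cancer treatment |
| SAP Section 11, added definition | No | 100 days after last dose, whatever treatment follows |
| SAP footnotes, Tables 14.3.1.1 to 14.3.1.3 | Yes | 100 days after last dose; no treatment cut-off printed |
| SAP Listing 16.2.7 note [2] | No | 100 days after last dose; no treatment cut-off printed |

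The SAP body differs from the protocol, and the SAP differs from itself. Because the added definition also works by occurrence, Tables 14.3.1.9 and 14.3.1.10 do not bring back the events that the main definition loses.

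**Step 2. How many tables carry the conflicting footnote.** The Table 14.3.1.1 shell also serves 14.3.1.9 (2 tables). The Table 14.3.1.2 shell serves itself and 16 further tables: 4 related, 1 serious, 4 serious related, 3 by consequence, 3 of special interest, and 14.3.1.10 (17 tables). Table 14.3.1.3 stands alone (1 table). Total: 2 + 17 + 1 = 20.

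**Step 3. Which records can have a pre-dose onset.** Protocol 8.3.1.1 collects AEs from the start of etigilimab. For serious events, "SAEs will be collected starting after signature of the informed consent". The same section sends medical occurrences between consent and first dose to Medical History. Appendix 4 makes an exacerbation of a pre-existing condition an AE, and says that updates to an event go on the form first completed for it. Three cases follow.

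- *Non-serious condition before dosing, worse on treatment.* It is held in Medical History, and the exacerbation is reported as an AE. If that AE is dated at the worsening, its onset falls after first dose and SAP 10.11.1 counts it. The documents do not state the dating rule.
- *Serious event with onset between consent and first dose (screening lasts up to 28 days), worse on treatment.* If it is updated on the same record, its onset stays before first dose and SAP 10.11.1 leaves it out.
- *Any AE entered with its true pre-dose onset date.* It is left out in the same way. The SAP's rule for missing or partial dates does not help, because the onset date is known.

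**Step 4. Direction and size.** With the same window, the records that meet an onset-only rule are a subset of those that meet an onset-or-worsening rule. Counts under SAP 10.11.1 can therefore only be equal to or lower than counts under the protocol definition. The documents give no number of pre-dose AE or SAE records and no rate of later grade increase, so the shortfall cannot be calculated.

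**The case against.** The best reply is that the collection rules already deal with most of this. AEs are collected only from the start of treatment, earlier occurrences go to Medical History, and an on-treatment exacerbation is an AE in its own right. The usual case, a baseline condition that flares on treatment, would then enter the tables with a post-dose onset. This largely stands. A reader might infer from SAP 10.11.1 that every event starting before dosing and worsening later disappears from the TEAE tables. The documents do not support that.

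The remaining case is also narrow. It needs a serious event within a screening period of at most 28 days, enrolment despite it, and later worsening on the same record. Protocol 3.2 excludes subjects with ongoing systemic infection at screening or with an important illness that the investigator judges to raise risk. The event would still appear in Listing 16.2.7. The SAP's sentence on pre-treatment events may itself be text carried over from another study, since 10.11.1 also refers to a viral challenge, which this trial does not have. It is weak evidence that such records are common.

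The Appendix 4 instruction to update the existing form does not settle whether a grade increase keeps the old onset date. Worsening on the same record is therefore possible under the documents, not established.

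There is also a practical objection. Listing 16.2.7 shows one start date, one stop date and one CTCAE grade per record, so a grade increase after first dose may not be programmable from those fields. This stands and shapes the fix.

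None of these points removes the contradiction between the SAP body, its footnotes and the protocol, or the missing entry in Section 11.

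**Conclusion.** The concern holds in limited form. SAP 10.11.1 narrows the protocol's TEAE definition, the footnotes of 20 tables still state the wider one, and the departure is not declared. The loss is confined mainly to serious events with onset between consent and first dose that are updated on the same record, and to any AE entered with its pre-dose onset date. It rests on the assumption that some worsening is entered on the existing record, which the documents neither require nor rule out.

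The number affected is unknown and probably small. A reader might be tempted to apply an assumed percentage to the planned 125 subjects. The documents give no rate, and 125 is a planned figure for a study that SAP 6.3 says was terminated before most cohorts needed their interim evaluation. What can be said is the direction: the error can only under-count. It is also wrong to say that the SAP uses onset with no other condition, since the 100-day and subsequent-treatment limits remain; what is missing is worsening. The point should be corrected before the tables are produced, mainly so that they apply the definition they print.

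**What to change.** In SAP 10.11.1, count an AE as treatment-emergent if its onset, or an increase in its CTCAE grade, falls on or after first dose and within the TEAE window. Limit the pre-treatment class to events that do not worsen.

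State how worsening is derived. Use dated grade changes or a separate record where the database holds them. Otherwise, treat a record with pre-dose onset as worsened when its outcome, grade or action taken shows worsening on treatment, and confirm each such case at the data review meeting.

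Make the footnotes of Tables 14.3.1.1 to 14.3.1.3 and Listing 16.2.7 note [2] print this same definition, including the subsequent-treatment cut-off. Tables 14.3.1.9 and 14.3.1.10 reuse two of those shells but ignore that cut-off, so they need their own footnote.

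If worsening cannot be derived from the data, keep the onset rule, remove worsening from the footnotes and declare the departure in Section 11.

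The cost is SAP wording, a small derivation and some record review. TEAE counts may rise slightly.
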